Visits and exams	
Every prostate cancer patient consecutively evaluated at the recruiting Centers and planned to receive radical exclusive or post-operative radiotherapy will be registered; this registration includes demographic and staging results data.
 
Only intermediate, high, very high patients will have, however, treatment and follow up CRF compiled, based on the inclusion criteria
 
Eligible patients will then receive all the information necessary to formulate their adhesion to the study and finally the physician will fill in the “Pretreatment” CRF that will include: Demographic Information; Anamnestic data; Initial diagnosis (date; PSA at diagnosis); Risk factors; Staging; Quality of life and symptoms caused by prostate cancer; General quality of life;
 
The choice of the treatment will be done based on commonly used international guidelines and on the specific internal protocol of each participating Center.
 
Since this study is observational, involved patients will be treated following good clinical practice and institutional policies procedures.
 
Clinical outcomes and variables, demographic features, dosimetric analysis and acute/late toxicities of both RT (with and without ENI) and ADT will be reported.

	
Follow-up visits on 1,3,6,12/18,24/30 and 36 months
 
Every patient will be contacted by the physicians to fill a CRF that will include: Vital state (mortality, date and causes of death) or loss to follow up; Last PSA value; Other treatments (drugs); type of RT and ADT treatment Acute and late toxicities; Biochemical Relapse with PSA value and date of last PSA; Quality of life and symptoms due to prostate cancer; General quality of life.
 
Survival status (mortality, date and cause of death) or exit from the study; If macroscopical recurrence or disease progression will occur, the radiological exams (if performed) will be reported; Further treatments received/planned after radiotherapy; The last available PSA;
 
Acute/Late toxicity
 
Genitourinary and gastrointestinal toxicity due to radiation therapy.
 
A CRF will be completed regarding: Technical characteristics of the radiation treatment; Quality of life and complications due to prostate cancer; General quality of life

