We propose a no-profit, multicenter observational study to collect data of consecutive patients treated with ENI both in the exclusive radical radiotherapy scenario and in the adjuvant postsurgical setting. Cases treated both with and without associated ADT will be recruited to evaluate Overall survival (OS) (that will be the main endpoint), Cause-specific (CSS) and Biochemical Relapse Free survival (bRFS), toxicity and Quality of Life (QoL) (the secondary endpoints).

Aims of the study

Clinical features and outcomes will be assessed as better detailed in the following lines:

1. To define the diffusion of the practice of treating pelvic lymph-nodes in patients affected by intermediate/high/very high risk non-metastatic prostate cancer (PCa) among Italian Radiation Oncology Centres, submitted to radical or post-operative radiotherapy;
2. To define the diffusion of the different radiotherapy techniques used to treat pelvic nodes and the other features of the radiation treatment;
3. To register prospectively biochemical and clinical failure, prostate cancer deaths and deaths for any cause in the population studied;
4. To register prospectively the toxicity due to radiotherapy and androgen deprivation therapy in patients treated with pelvic nodes radiotherapy;
5. To compare clinical outcomes and toxicities observed in the different clinical and therapeutic subgroups with the corresponding historical data relative to PCa patients treated with radiotherapy with or without elective pelvic nodal irradiation, already available in the existing AIRO (Italian Society of Radiation Oncology) databases;

6. To exploit the collected data to define the need and the features of a prospective randomized trial evaluating the efficacy of elective pelvic nodal irradiation in patients with intermediate/high/very high risk non-metastatic prostate cancer.
7. The data obtained from the present observational study will be helpful for designing a subsequent randomized controlled trial.

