In summary, the study aims at the definition of survival, toxicity and QoL data in a representative sample of intermediate, high and very high risk prostate cancer patients consecutively recruited in Italian Radiation Oncology Centres over two years. Parameters considered will be OS, CSS and bRFS, toxicity (rectal, bladder, bowel toxicity, according to CTCAE v.4 scale) and QoL (according to the SF-12 scale and UCLA-PCI scale). Primary end point will be OS. Secondary endpoints will be CSS, bRFS, gastrointestinal and genitourinary toxicity, QoL deterioration.

Study Design

This is a prospective, multicenter, observational cohort study aimed to describe the advantage/disadvantage of different treatments of patients with intermediate/high/very high risk prostate cancer, through a web-based database.

Study Duration

The recruitment period, taking into account the needed sample size (*v.infra*) will be of two years, followed by three-year follow up period for each patient, with an accrual of at least 400-500 patients.

Population, Procedures

The study will include all consecutive patients affected by intermediate, high or very high-risk prostate cancer that fit the inclusion criteria and who are evaluated at each Centre involved in the study. Patients may have already undergone or not to radical prostatectomy and/or pelvic lymphadenectomy.

Inclusion criteria

- Men older than or aged 18 years;
- Histologically confirmed intermediate, high or very high risk prostate cancer patients (NCCN classification: Intermediate Risk T2b and T2c or Gleason Score 7 or PSA value between 10 and 20 ng/mL; High risk: T3a or Gleason score 8-10 or PSA > 20 ng/ml; Very high risk: T3b-T4 or patients with multiple adverse risk factors reported in the high risk category that may be shifted in the very high risk group
- Patients eligible for -and actually submitted to- radical radiotherapy treatment (+/- androgen deprivation) or adjuvant radiotherapy treatment after surgery (radical prostatectomy +/- pelvic lymphadenectomy);
- No other synchronous or previous malignant tumor other than skin basal cell carcinoma;
- Patients able to understand and sign the appropriate informed consent;
- Patients able to fill the QoL questionnaire;

Exclusion criteria

- Patients aged less than 18;

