Centers involved will identify all the eligible cases with biopsy proven prostate adenocarcinoma. Patients who are candidate to get involved in the study will be contacted by the physician in charge of the study for each Center. **Every** prostate cancer patient consecutively evaluated at the recruiting Centers and planned to receive radical exclusive or post-operative radiotherapy will be registered; this registration includes demographic and staging results data; only intermediate, high, very high patients will have, however, treatment and follow up CRF compiled (both treated with or without ENI; +/- ADT).

Eligible patients will then receive all the information necessary to formulate their adhesion to the study and finally the physician will fill in the “Pretreatment” Case Report Form (CRF) that will include:

- Demographic Information (date of birth, study title, civil state, working information);
- Another person (relatives, friends,...) as a contact to minimize follow up loss;
- Anamnestic data (height, weight, smoking habit, comorbidities, Cumulative Illness Rating Scale [44], Attachment 1);
- Initial diagnosis (date; PSA at diagnosis);
- Risk factors;
- Staging (clinical TNM, date of biopsy, Gleason score, total number of samples, number of positive samples);
- Quality of life and symptoms caused by prostate cancer (using Italian UCLA Prostate Cancer Index) [45, 46];
- General quality of life (SF-12 Standard V1) [47].

The choice of the treatment will be done based on commonly used international guidelines and on the specific internal protocol of each participating Center.

Since this study is observational, involved patients will be treated following *good clinical practice* and institutional policies procedures.

Clinical outcomes, (such as overall survival and biochemical relapse free survival) and variables, demographic features, dosimetric analysis and acute/late toxicities of both RT and ADT will be reported.

Phase 3: Follow-up (1, 3, 6, 12, 18, 24, 30, 36 months)

After the end of the radiotherapy treatment patients will be evaluated 1, 3, 6, 12, 18, 24, 30 and 36 months since the last session.

Every patient will be contacted by the physicians to fill a CRF that will include:

- Vital state (mortality, date and causes of death) or loss to follow up;
- Last PSA value;

- Other treatments (drugs);

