- Treatment : type of treatment, start date, PSA value before treatment; if surgery type of surgery and pathological TNM, margins, Gleason Score, number of positive lymph nodes; if external RT (intent, modality, technique, dose/fraction, volumes, concomitant hormonal therapies); if brachytherapy (type, intent, dose); if hormone therapy (type of drugs, start and end date, total duration);
- Acute and late toxicities;
- Biochemical Relapse with PSA value and date of last PSA;
- Quality of life and symptoms due to prostate cancer (Italian UCLA-PCI);
- General quality of life SF-12.

Toxicity and response evaluation

The enrolled patients will undergo the first follow up visit one month after the end of radiotherapy. On that occasion, clinical examination will be performed and previously prescribed blood tests, if required, will be evaluated. Genitourinary and gastrointestinal toxicity due to radiation therapy for prostate cancer will be reported according to the NCI Common Terminology Criteria for Adverse Events (CTCAE) version 4 for adverse event (AE) reporting. The CTCAE version 4 is identified and located on the CTEP web site at:

http://ctep.cancer.gov/protocolDevelopment/electronic_applications/ctc.htm [48]

In addition, a Case Report Form (CRF) will be completed (see Attachment 2), regarding:

- Technical characteristics of the radiation treatment (dose, volume, technique, association or not with hormonal therapy);
- Quality of life and complications due to prostate cancer (according to Italian UCLA-PCI) [45, 46];
- General quality of life (SF-12 Standard V1) [47].

Thereafter patients will be evaluated at 3-months, 6-months and 12-months after the end of radiotherapy, and then every 6 months for at least 24 months. During all those scheduled follow up visits, PSA level (jointly with testosterone, in case of association with hormonal therapy) and

previously prescribed blood texts if required, will be evaluated. Patients will undergo clinical examination, and genitourinary and gastrointestinal toxicity will be assessed according to the CTCAE v4.0 classification scale). In addition, a CRF (see Attachment 3) will be completed at each visit, regarding:

- Survival status (mortality, date and cause of death) or exit from the study;
- If macroscopical recurrence or disease progression occurred, the radiological exams (if performed);
- Further treatments received/planned after radiotherapy;
- The last available PSA;

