ATTACHMENT 2 – 1 MONTH FOLLOW UP

Date of starting treatment	_____ / _____ / _____ day month year
Date of ending treatment	_____ / _____ / _____ day month year
Pre-treatment PSA	_____ . _____ ng/mL

External Beam Radiation Therapy	
Aim of Radiation Therapy	1 Radical exclusive 2 Adjuvant 3 Salvage post-operative 4 Other, specify _____
Modality	1 IGRT 2 Non IGRT
Technique	1 3D-CRT 2 IMRT (step and shoot) 3 IMRT (volumetric) 4 SBRT (stereotactic body radiotherapy)
Technique-2	

	1 Sequential RT 2 SIB IMRT
Dose/fraction V1	__ , __ Gy
Total dose V1	__ , __ Gy
Dose/fraction V2	__ , __ Gy
Total dose V2	__ , __ Gy
Dose/fraction V3	__ , __ Gy
Total dose V3	__ , __ Gy
Rectum V25	Value
Rectum V50	Value
Rectum V60	Value
Rectum D50	Value
Rectum Dmax	Value
Bladder Dmax	Value
Bladder D50	Value
Bladder V50	Value
Bladder V70	Value
Penile Bulb Dmax	Value
Penile Bulb D90	Value
Small bowel V15 (contouring individual bowel loops)*	Value
Small bowel V45 (contour peritoneal space)*	Value
*contouring of the peritoneal space is required for all patients, optional contouring individual bowel loops	
Target volume V1	1 Prostate only 2 Prostate and basis of seminal vesicles 3 Prostate and seminal vesicles 4 Prostate plus pelvis (nodal volume) 5 Prostate and seminal vesicles and pelvis (nodal volume)

Target volume V2	1 Prostate plus pelvis 2 Nodal volume only 3 Prostate and seminal vesicles 4 Prostate and basis of seminal vesicles 5 Prostate only
Target volume V3	1 Nodal volume only 2 Prostate and seminal vesicles 3 Prostate and basis of seminal vesicles 4 Prostate only
Association with hormonal therapy	1 Radiotherapy alone 2 Radiotherapy and neoadjuvant hormonal therapy (before radiation therapy) 3 Radiotherapy and adjuvant hormonal therapy (after radiation therapy) 4 Radiotherapy and neoadjuvant + adjuvant hormonal therapy

Hormonal therapy					
Type of hormonal therapy	1	ADT			
	2	Periferic Antiandrogen If antiandrogen, specify the type: 1 Acetate ciproterone 2 Bicalutamide 3 Flutamide 4 Other, specify _____			
	3	If antiandrogen, specify the dose: _____			
	4	LHRH Agonist (or GnRH)			
	5	LHRH Antagonist (or GnRH)			
		Other, specify _____			
Date of starting hormonal therapy	day	/	month	/	year

Acute Toxicities

Rectal Acute Toxicity (Grade)

Date Tox.

Urinary Acute Toxicity (Grade)

Date Tox.

Small Intestine Acute Toxicity
(Grade)

Date Tox.

GI Acute Toxicity (small bowel)

(see Table 1)

select (1=G0, 2=G1, 3=G2, 4=G3, 5=G4, 6=Unknown)

Date yyyy-mm-dd

Rectal Acute Toxicity

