ATTACHMENT 3 – 3, 6, 9, 12, 18, 24, 36 MONTHS FOLLOW UP

	
1 He does not adhere anymore for health reasons, specify _____
 
2 He is not interested anymore to take part in the study
 
3 He is not traceable

Does the patient still undergo Hormonal Therapy?	
1. Yes
 
If yes: (FILL IN POINT 4 BELOW)
 
0 No
 
If no: Date of ending hormonal therapy  / /  day month year

Has he developed new comorbidities? (It is possible to fill in more than one option)	
0 . No
 
1 . Yes
 
If yes:
 
 1 Cardiac (specify _____) 2 Vascular (including hypertension) 3 Pulmonary (specify _____) 4 Eye, ear, nose, throat, larynx 5 Gastro-intestinal (specify _____) 6 Hepatic (liver only) 7 Renal (kidneys only) 8 Musculo-skeletal (specify _____) 9 Intertegumentary (skin) 10 Neurological (specify _____) 11 Endocrine-metabolic (specify _____) 12 Cognitive-psychiatric, behaviour 13 Genito-urinary (ureter-genitals) (specify _____) 14 Other malignancies (including Haematopoietic malignancies)

	15 Other, specify _____	
Has he undergone further treatments for prostate cancer, subsequent to those reported in Attachment 1 (1-month follow up)?	0 No	
	1 Yes	
	If yes:	
	1	Surgery
	2	External Beam Radiation Therapy
	3	Brachytherapy
	4	Radiometabolic Therapy
	5	Hormonal Therapy
	6	Focal Therapy
7	Chemotherapy	
8	Others, specify _____	

If he has undergone further treatments, specify:

Date of starting the new treatment |__|/|__|/|__|_|_|

day month year

PSA before starting the new treatment |__|_|_|_|. |__|_|_| ng/mL

 External Beam Radiotherapy	
Aim of Radiotherapy	1 Palliative
	2 Other, specify_____
Modality	1 IGRT
	2 Non IGRT
Technique	1 3D-CRT

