
Acute Toxicities

Rectal Acute Toxicity (Grade)		Date Tox.	
Urinary Acute Toxicity (Grade)		Date Tox.	
Small Intestine Acute Toxicity (Grade)		Date Tox.	

GI Acute Toxicity (small bowel)

(see Table 1)

select (1=G0, 2=G1, 3=G2, 4=G3, 5=G4, 6=Unknown)

Date yyyy-mm-dd

Rectal Acute Toxicity

select (1=G0, 2=G1, 3=G2, 4=G3, 5=G4, 6=Unknown)

Date yyyy-mm-dd

Urinary Acute Toxicity

select (1=G0, 2=G1, 3=G2, 4=G3, 5=G4, 6=Unknown)

Date

Late Toxicity bladder/ rectum

select (1=Yes, 2=No, 3=Unknown)

Date yyyy-mm-dd

Proctitis

select (1=G0, 2=G1, 3=G2, 4=G3, 5=G4, 6=I Unknown)

Date yyyy-mm-dd

Cystitis

select (1=G0, 2=G1, 3=G2, 4=G3, 5=G4, 6= Unknown)

Date yyyy-mm-dd

Impotence

select (1=No, 2=Yes pre RT, 3=Yes post RT, 4= Unknown)

Date yyyy-mm-dd

Incontinence

select (1=No, 2=Yes pre RT, 3=Yes post RT, 4=Unknown)

TABLE 1 – Toxicity

RECTAL/SMALL BOWEL Acute TOX

G0: No Toxicity

G1: Increased alvus frequency not requiring any treatment. Rectal pain or abdominal pain not requiring any painkillers

G2: Diarrhoea, mucositis, rectal pain or abdominal pain requiring painkillers

G3: Diarrhoea requiring parenteral supportive care, severe mucositis or haematological alterations requiring treatment. Abdominal distension

G4: Acute or subacute obstruction, fistula or perforation, haemorrhage requiring blood transfusion. Abdominal pain or tenesmus requiring ileostomy

BLADDER Acute TOX

G0: No Toxicity

G1: Low urinary tract symptoms (LUTS) and dysuria not requiring any treatment

G2: LUTS, dysuria and urgency requiring treatment or anaesthetics

G3: Severe LUTS, urgency, dysuria, pelvic pain or bladder spasms and haematuria

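### Aim 4 promises prospective registration of ADT toxicity, but every graded toxicity item on the printed forms is a pelvic effect, so the ADT half of the aim can be met only indirectly and incompletely

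*Combined protocol and SAP*

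**What the plan says.** The promise appears three times in the combined protocol and SAP.

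- Aims of the study, aim 4: "To register prospectively the toxicity due to radiotherapy and androgen deprivation therapy in patients treated with pelvic nodes radiotherapy".
- Synopsis, Visits and exams: "acute/late toxicities of both RT (with and without ENI) and ADT will be reported".
- Population, Procedures, Phase 2: "dosimetric analysis and acute/late toxicities of both RT and ADT will be reported".

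Aim 5 then sets the toxicities seen in the clinical and therapeutic subgroups against historical data from existing AIRO databases.

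The operational text is narrower. The summary that closes the aims lists the parameter as "toxicity (rectal, bladder, bowel toxicity, according to CTCAE v.4 scale"). The section on toxicity and response evaluation says "Genitourinary and gastrointestinal toxicity due to radiation therapy for prostate cancer will be reported according to the NCI" CTCAE version 4. Both name pelvic effects only, and the second ties them to radiation.

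The forms follow the narrower text. Attachments 2 and 3 print the same toxicity block, opening with acute rectal, urinary and small-intestine grades. Separately, Attachment 3 asks "Has he developed new comorbidities", with a 15-category list to tick.

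**The concern.** A prospective study can report only what its forms capture at the visit. If ADT effects have no graded and dated field, they are recorded when a clinician happens to think of them, while radiation effects are prompted and graded every time. The two treatments' harms are then measured with different sensitivity.

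This matters because the study recruits patients with and without ADT, says that it will describe the advantages and disadvantages of different treatments, and compares toxicity by therapeutic subgroup. The Background describes adjuvant ADT of 2 to 3 years as typical in high and very high risk disease. Follow-up lasts 36 months after radiotherapy, so in such patients ADT could cover from 24/36 (two thirds) to 36/36 (all) of the observation period. Information on graded severity and onset that is missed during that time cannot be reliably rebuilt afterwards.

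**Working it through.** No toxicity rate, toxicity sample size or toxicity precision is given, so there is no figure to reproduce on this point. The plan's one design figure concerns overall survival: 0.8 ± 1.96 × √(0.8 × 0.2 / 400) = 0.8 ± 0.039, or 0.761 to 0.839. That agrees with the stated 0.76 to 0.84 and has no bearing here. The check is a field-by-field reading of the forms.

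**Step 1. Toxicity-related fields as printed**

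| Field | Attachments | Graded | Date field | Attributed to ADT |
|---|---|---|---|---|
| Acute rectal | 2, 3 | yes | yes | no |
| Acute urinary | 2, 3 | yes | yes | no |
| Acute small bowel | 2, 3 | yes | yes | no |
| Late bladder/rectum (yes, no, unknown) | 2, 3 | no | yes | no |
| Proctitis | 2, 3 | yes | yes | no |
| Cystitis | 2, 3 | yes | yes | no |
| Impotence (no, pre RT, post RT, unknown) | 2, 3 | no | yes | no |
| Incontinence (same codes) | 2, 3 | no | none printed | no |
| New comorbidities | 3 only | no | none printed | no |

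Graded items: 3 acute + 2 late = 5, all pelvic. Table 1 of the forms defines grades for these only. Items graded for, or attributed to, ADT: 0. The synopsis cites CTCAE version 4 for adverse event reporting in general, but no printed form has a general adverse event field.

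**Step 2. What could stand in for ADT toxicity**

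- *New comorbidities.* At least five of the 15 categories could hold systemic ADT effects: cardiac, vascular, musculo-skeletal, endocrine-metabolic and cognitive-psychiatric. There is also a free-text category. The item is absent from the 1-month form, and its categories do not map one to one onto the baseline CIRS. For example, CIRS scores hypertension separately, while the follow-up list puts it under vascular. It asks about new conditions, not about worsening of existing ones.
- *Impotence.* Attachment 2 allows neoadjuvant and adjuvant hormonal therapy. Impotence starting under neoadjuvant ADT would be coded as before radiotherapy, and impotence starting under adjuvant ADT as after it. Neither code separates ADT from surgery or radiation.
- *UCLA-PCI and SF-12.* Sexual function, energy and mood are asked at baseline and at follow-up. The protocol treats these as quality of life, not as toxicity.
- *ADT exposure.* Type and start date are in Attachment 2; ongoing use and end date are in Attachment 3. Exposure is therefore reasonably well recorded.
- *Testosterone.* It is to be evaluated at visits when ADT is given, but no printed form has a field for it.

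**Step 3. Promise against data.** With exposure dates and the indirect items, a crude comparison of patients with and without ADT is possible for new organ-system conditions, sexual function, energy and mood. Grade, onset and attribution of ADT effects are not available, apart from an impotence date that can be set beside the ADT dates.

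**The case against.** The strongest reply is that ADT toxicity is not an endpoint. The secondary endpoint is rectal, bladder and bowel toxicity, which the forms grade; the primary endpoint is overall survival. On this view the gap is loose wording in one descriptive aim and two procedural sentences. That stands as a limit on importance, but not as an answer: the aim is stated, the reporting promise is made twice more, and the forms do not deliver it.

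A second reply is that the indirect items are more useful than they look. This also stands in part. A reader might infer that aim 4 cannot be answered at all for ADT, or that ADT would appear almost free of toxicity. The documents support neither: the comorbidity list, the ADT dates, the UCLA-PCI and the SF-12 give some information, and no rate is available to size the shortfall.

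Two further inferences should be resisted. One is that all ADT-related sexual effects would be filed as following radiotherapy. The impotence item has a code for onset before radiotherapy and a date, and the UCLA-PCI sexual items are not tied to radiotherapy. The other is that the second open question, whether nodal irradiation is still needed once ADT is given, is compromised. ADT is given on both sides of that comparison, and the added harm of nodal irradiation is pelvic, which is graded.

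Finally, the printed forms may be incomplete. Attachment 3 appears to begin partway through a table, and the web database is not shown. The toxicity block itself is printed in both attachments.

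**Conclusion.** The mismatch holds. Three statements promise ADT toxicity; all five graded items are pelvic, and none is graded for or attributed to ADT. The ADT half of aim 4 can be met only indirectly and incompletely, and the toxicity comparison by therapeutic subgroup in aim 5 inherits that limit. Under-recording of ADT effects is likely because nothing on the forms prompts for them as ADT toxicity. That is a judgement from the form design; the documents give no expected rates from which to compute a bias.

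The radiotherapy half of aim 4, the gastrointestinal and genitourinary toxicity endpoint and overall survival are unaffected. The point is therefore one of matching an aim to its data, worth correcting because it is cheap. It assumes that the web database contains no ADT toxicity fields beyond the printed forms.

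**What to change.** Preferred: add to Attachments 2 and 3 a short CTCAE v4 block, with grade and onset date, of ADT-related terms chosen by the study group. Complete it in all patients, so that those not receiving ADT provide the comparison. Add a grade and an onset date to the new-comorbidity item in Attachment 3. The cost is a few fields at visits already scheduled and slightly longer data entry; no patient's treatment changes.

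Otherwise: restrict aim 4, the synopsis text under Visits and exams and the Phase 2 reporting sentence to the toxicity actually collected, and describe comorbidity, UCLA-PCI and SF-12 data as indirect information on ADT. This costs only a text edit, but gives up the ADT half of the aim.

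Before either change, check the web database for fields that the printed forms do not show.

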- Patients not eligible for -and actually not submitted to- radical radiotherapy treatment (+/- androgen deprivation) or adjuvant radiotherapy treatment after surgery (radical prostatectomy +/- pelvic lymphadenectomy);
- Low risk prostate cancer (<T2b and T2c or < Gleason Score 7 or PSA value < 10 ng/mL);
- Patients with synchronous or previous malignancy other than skin basal cell carcinoma;
- Patients able to understand and sign the appropriate informed consent (IC) who decide not to subscribe IC;
- Patients not able to understand and sign the appropriate informed consent (IC)

- Patients unable to fill the QoL questionnaire.

Involved Centers

The Radiation Oncology Unit of the University and Spedali Civili of Brescia will be the promoter and coordinator Center. From previous studies of the AIRO Prostate Study Group it can be inferred that at least 15-20 Radiation Oncology Centers from different areas of Italy will be involved; this will assure the widest and homogenous participation throughout the country.

Accrual and timeline

The study will start when a sufficient number of Centres will have obtained EC approval.

Estimated total time of recruitment is 2 years. It will be followed by a three years period of follow up for each patient.

Phase 1: Establishment of the network of Centers involved in the study

During this phase the study protocol has to be shared as much as possible within the Italian radiation oncology community in order to identify and involve as many as possible interested Centres throughout the country.

This will be done in official sessions of the Prostate Cancer Study Group (PCSG) of AIRO meetings.

Each center that will become a part of the study will identify a referring physician who must accomplish the systematic recruitment of eligible patients and provide the collection of data on the appropriate *web portal* established in Brescia.

Phase 2: Activation and recruitment of eligible cases

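### A questionnaire needed only for a secondary endpoint decides who enters the overall survival cohort, which limits the claim of a representative sample; the effect is unknown and probably small

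*Combined protocol and SAP*

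**What the plan says.** Entry to the study requires "Patients able to fill the QoL questionnaire" (Inclusion criteria), and the Exclusion criteria repeat the rule as "Patients unable to fill the QoL questionnaire". The synopsis carries both. Nothing confines the rule to the QoL analysis. Men who cannot understand and sign the consent form are excluded under a separate bullet.

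On endpoints, the summary at the end of Aims of the study says "Primary end point will be OS", and then "Secondary endpoints will be CSS, bRFS, gastrointestinal and genitourinary toxicity, QoL deterioration". The same paragraph describes the target as survival, toxicity and QoL "in a representative sample of intermediate, high and very high risk prostate cancer patients consecutively recruited" in Italian centres.

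Population, Procedures is more guarded: "The study will include all consecutive patients affected by intermediate, high or very high-risk prostate cancer that fit the inclusion criteria". Under Phase 2, every prostate cancer patient planned for radical or post-operative radiotherapy is registered, but "this registration includes demographic and staging results data". The synopsis ties the treatment and follow-up case report forms (CRFs) to the inclusion criteria. The Phase 2 text limits those forms by risk group and does not repeat the link.

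Vital status, cause of death, PSA and toxicity are collected by the physician (Phase 3; Toxicity and response evaluation). The end of the latter section allows a nurse to help a patient with the questionnaires.

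**The concern.** A man who can consent, receives radiotherapy and has his survival status recorded by his physician has everything OS requires. The rule still removes him because he cannot supply data for one secondary endpoint. If such men tend to have cognitive, visual or neurological impairment, their survival may be worse than that of the men who remain. The OS estimate would then be too high for the population named in the aims.

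The confidence interval does not show this kind of error, and a larger sample does not reduce it. Statistical Analyses contains no comparison of registered with enrolled men that would bring it to light. The population matters because the aims include comparison with historical data and use of the results to design a randomised trial. For both, the reader must know whom the estimate describes.

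**Working it through.** **1. The plan's own figure.** Inputs from Sample size: n = 400, 5-year OS p = 0.80, stated 95% interval 0.76-0.84. With the normal approximation and no censoring:

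- SE = √(0.80 × 0.20 / 400) = 0.020
- half-width = 1.96 × 0.020 = 0.039
- interval = 0.761 to 0.839

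This rounds to the stated interval, so the figure reproduces. It covers sampling error only.

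**2. Which data need the questionnaire.**

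| Endpoint | Source in the protocol | Questionnaire needed? |
|---|---|---|
| OS, CSS | vital status and cause of death on the CRF | no |
| bRFS | PSA and relapse entries on the CRF | no |
| Toxicity | physician grading | no |
| QoL | SF-12 and UCLA-PCI | yes |

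Only the last row justifies the criterion, but the criterion governs all four.

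**3. What is kept on excluded men.** Demographic and staging data from registration. The pretreatment CRF, which holds the comorbidity scale, is completed for eligible patients. Follow-up forms depend on the inclusion criteria, according to the synopsis. Excluded men therefore have no vital status, and their survival cannot be recovered at analysis.

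**4. Illustrative size.** Let f be the share of otherwise eligible, consenting men removed by this rule alone, and S their 5-year OS. The documents give neither, so both are assumptions. With OS of 0.80 in enrolled men:

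bias = 0.80 − [(1 − f) × 0.80 + f × S] = f × (0.80 − S)

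| f | S | Bias in OS | Share of the 4-point half-width |
|---|---|---|---|
| 2% | 0.7 | 0.02 × 0.10 = 0.002 (0.2 points) | 5% |
| 5% | 0.6 | 0.05 × 0.20 = 0.010 (1.0 point) | 25% |
| 10% | 0.6 | 0.10 × 0.20 = 0.020 (2.0 points) | 50% |
| 10% | 0.5 | 0.10 × 0.30 = 0.030 (3.0 points) | 75% |

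For the bias to equal 4 points, f would have to be 0.04 / 0.20 = 20% at S = 0.6, or 0.04 / 0.30 = 13% at S = 0.5. If S equals 0.80, the bias is zero.

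**5. Effect on coverage.** With SE 0.020, a bias b shifts the interval by b / 0.020 standard errors. Coverage of the target-population OS is Φ(1.96 − b/0.020) − Φ(−1.96 − b/0.020). This gives about 92% at b = 0.010 and 83% at b = 0.020, against a nominal 95%.

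**The case against.** The strongest case against is that the affected group is narrow. This rule alone removes only men who receive radical or adjuvant radiotherapy, can understand and sign consent, and still cannot complete two short questionnaires with a nurse at hand. Nurse help should cover many visual, manual and literacy limits, and men too impaired to consent are already out. A share of 10% has no support in the text. This stands, and it is why the effect is probably small. It does not justify the rule: if the rule removes almost nobody, deleting it costs almost nothing. Nor does the criterion say whether inability is judged with or without help, so the expected 15-20 centres may apply it differently.

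It is also fair to say that requiring questionnaire ability limits missing QoL data, and that the cohort is defined as consecutive patients who meet the criteria, so there is no flat contradiction with the claim of representativeness. Other rules, such as exclusion for a previous malignancy, also select. Removing this one would not by itself make the sample representative. But this one is avoidable, because the QoL aim can be served by a separate analysis set.

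A reader might infer three stronger things that the documents do not support:

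- **That OS certainly loses frailer, older or less educated men.** The documents do not describe the excluded men. Language or literacy may be the reason. The pretreatment CRF (Attachment 1) provides for patients with no educational qualification, very serious comorbidity and cognitive impairment, so such men are not barred as a class.
- **That these men disappear from the study altogether.** They are registered. What they lack is outcome data.
- **That comparisons with and without nodal irradiation are biased.** The rule applies alike to all treatment groups, and regression adjustment is planned. There it mainly limits generalisability.

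**Conclusion.** The point holds as a limited one. A requirement of one secondary endpoint controls entry to the primary OS cohort and to every other outcome, and registration does not make good the loss. This may remove some men with worse survival, and so it limits the claim of a representative sample.

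The size cannot be determined from the documents. The range of 0.2 to 3.0 points rests entirely on an assumed share of 2-10% and an assumed 5-year OS of 0.5-0.7 in the excluded men. Its upper end combines the two most adverse values, and the whole range lies below the stated 4-point half-width. These figures also use the 5-year horizon of the sample-size section; scheduled follow-up runs to 36 months, where the difference would probably be smaller. This is a cheap improvement to the design, not a threat to the study's main result.

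**What to change.** - Delete the questionnaire criterion from study eligibility in the synopsis and in the Inclusion and Exclusion criteria. Apply it only to the QoL analysis set.
- Analyse OS, CSS, bRFS and toxicity in all consenting men who are otherwise eligible.
- At each visit, record whether the questionnaire was completed and, if not, why.
- Add to Statistical Analyses a comparison of registered with enrolled men in the eligible risk groups, using the demographic and staging data already collected, with reasons for non-enrolment. This describes the selection but cannot correct OS, because registration holds no vital status.
- Make the Phase 2 text and the synopsis agree on who receives treatment and follow-up forms.

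The cost is a small amendment and some missing QoL data. The OS cohort would, if anything, be slightly larger. If recruitment has already closed, restrict the representativeness statement in the aims, and in any report, to men able to complete the questionnaire, and still report the comparison of registered with enrolled men.
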